#### **10.2.3.1.5 Safety Monitoring Plan**

Subject safety will be routinely monitored as defined in the Amgen's safety surveillance and signal management processes.

#### **10.2.3.1.6 Pregnancy and Lactation**

Details of all pregnancies and/or lactation in female subjects and female partners of male study subjects will be collected after the start of study treatment, and until 6 months for female study subjects and 8 months for female partners of male study subjects after the last dose of AMG 404.

If a pregnancy is reported, the investigator is to inform Amgen within 24 hours of learning of the pregnancy and/or lactation and is to follow the procedures outlined in Section 13.6. Amgen Global Patient Safety will follow-up with the investigator regarding additional information that may be requested.

Abnormal pregnancy outcomes (eg, spontaneous abortion, fetal death, stillbirth, congenital anomalies, ectopic pregnancy) are considered serious adverse events.

Further details regarding pregnancy and lactation are provided in Section 13.6.

### **10.2.3.2 Vital Signs**

The following measurements must be performed: systolic/diastolic blood pressure (BP), respiratory rate, heart rate and temperature. Subject must be in rested and calm state for at least 5 minutes before BP assessments are conducted. The position selected for a subject should be the same that is used throughout the study and documented on the vital sign eCRF. Record all measurements on the vital signs eCRF.

The temperature location selected for a subject should be the same that is used throughout the study and documented on the vital signs/temperature eCRF. Vital signs will be recorded by the investigator or designee at screening and time points specified in the Schedule of Activities (see Section 3.2).

Abnormal measurements may be repeated at the discretion of the investigator and must be reported on the corresponding eCRF page. When vital signs and blood sample collection occur at the same time, vital signs should be performed before blood samples are drawn.

### **10.2.3.3 Electrocardiograms (ECGs)**

Subject must be in a supine position in a rested and calm state for at least 5 minutes before ECG assessment is conducted. If the subject is unable to be in the supine position, the subject should be in the most recumbent position as possible.

ECGs should be performed in accordance with the Schedule of Activities (see Section 3.2), in triplicate, in a standardized method, prior to blood draws or other invasive procedures. Each ECG must include the following measurements: QRS, QT, QTc, RR, and PR intervals.

All ECGs will be triplicates with each tracing approximately 30 seconds apart and run consecutively.

For subjects enrolled to Cohorts 1, 2 and 4, triplicate ECGs must be performed at

- Screening
- Cycle 1: day 1 predose, end of infusion, and 4 hours postdose
- Cycle 2: day 1 end of infusion
- Cycle 3: day 1 end of infusion
- Cycle 4: day 1 end of infusion
- Cycle 5: day 1 end of infusion
- Beginning with Cycle 6, ECGs will be done if clinically indicated

For subjects enrolled to Cohort 3, and Cohorts **6-9** triplicate ECGs must be performed at screening and then as clinically indicated.

The PI or designated sub-investigator will review all ECGs. ECGs will be transferred electronically to a central Amgen vendor. Once reviewed and signed by PI or sub-investigator, the original ECG tracing will be retained with the subject's source documents. At the request of the sponsor, a copy of the original ECG will be made available to Amgen. Standard ECG machines will be provided by Amgen for all study-related ECG requirements.

#### **10.2.4 Clinical Laboratory Assessments**

Refer to Section [13.2](#) for the list of clinical laboratory tests to be performed and to the Schedule of Activities (Section [3.2](#)) for the timing and frequency. All tests (except for PK XXXXXXXXXX) are to be performed at a local laboratory and test results are to be recorded in the eCRF. Additional safety laboratory assessments may be performed if clinically indicated at the discretion of the investigator.

The investigator is responsible for reviewing laboratory test results and recording any clinically relevant changes occurring during the study in the Event CRF. The investigator must determine whether an abnormal value in an individual study subject represents a clinically significant change from the subject's baseline values. In general, abnormal laboratory findings without clinical significance (based on the investigator's judgment) are not to be recorded as adverse events. However, laboratory value changes that require treatment or adjustment in current therapy are considered adverse events. Where applicable, clinical sequelae (not the laboratory abnormality) are to be recorded as the adverse event.

All protocol-required laboratory assessments, as defined in Section [13.2](#), must be conducted in accordance with the laboratory manual and the Schedule of Activities (Section [3.2](#)).

##### **10.2.4.1 Pregnancy Testing**

[figure not shown]
A serum pregnancy test must be performed at screening and within 48 hours of cycle 1 dose of AMG 404; beginning with cycle 2, a urine or serum pregnancy test must be

performed within 48 hours prior to the AMG 404 dose for females of childbearing potential (see Schedule of Activities Section 3.2).

Additional on-treatment pregnancy testing may be performed at the investigator's discretion or as required per local laws and regulations.

Note: Females who have undergone a bilateral tubal ligation/occlusion should have pregnancy testing per protocol requirements. (If a female subject, or the partner of a male subject, becomes pregnant it must be reported on the Pregnancy Notification Form, see Figure 13-3). Refer to Section 13.6 for contraceptive requirements.

#### **10.2.5 Pharmacokinetic Assessments**

[figure not shown]
All subjects enrolled will have pharmacokinetic samples assessed.

Blood samples will be collected for measurement of serum concentrations of AMG 404 as specified in the Schedule of Activities (Section 3.2),

Instructions for the

collection and handling of biological samples will be provided by the sponsor. The actual date and time (24-hour clock time) of each sample will be recorded.

[figure not shown]

[figure not shown]
### 10.2.7 Antibody Testing Procedures

[figure not shown]
Blood sample(s) for antibody testing are to be collected according to the time points specified in the Schedule of Activities (Section 3.2) for the measurement of anti-AMG 404 antibodies.

[figure not shown]
Samples testing positive for binding antibodies to AMG 404 may be further characterized. Additional blood samples may be obtained to rule out anti-AMG 404 antibodies during the study.

[figure not shown]
Subjects who test positive for anti-AMG 404 antibodies at the final scheduled antibody time point and have clinical sequelae that are considered potentially related to an anti-AMG 404 antibody response will be asked to return for additional follow-up testing. Sample collection and testing will occur approximately every 3 months from the safety follow up visit until: (1) anti-AMG 404 antibodies are no longer detectable; or (2) the subject has been followed for a period of at least 1 year ( $\pm$  4 weeks) post administration of AMG 404. All follow-up results, both positive and negative, will be communicated to the sites. More frequent testing (eg, every month) or testing for a longer period of time may be requested in the event of safety-related concerns. Refer to the Schedule of Activities (Section 3.2), as applicable, for specific time points, and the laboratory manual for detailed collection and handling instructions.

## 11. Statistical Considerations

### 11.1 Sample Size Determination

Up to 275 evaluable subjects will be enrolled in this study. Approximately, 2 to 4 DLT-evaluable subjects will be enrolled in Cohort 1. Approximately, 6 to 9 DLT-evaluable subjects will be enrolled each in Cohort 2. Approximately, 20 subjects will be enrolled each in Cohorts 3, 4, and 6 all outside of China. Approximately, 12 subjects will be enrolled to Cohort 5 in China/Taiwan/Hong Kong. Approximately, 40 subjects, respectively, will be enrolled to Cohort 7, Cohort 8, and Cohort 9.

[figure not shown]
With 2 subjects in Cohort 1, there is a 36 – 55% probability of observing at least 1 DLT. With 4 subjects in Cohort 1, there is a 59 - 80% probability of observing at least 1 DLT if the true DLT rate is 20 – 33%.

Similarly, with 6 subjects per cohort, there is a 74 - 91% probability of observing at least 1 DLT. With 9 subjects per cohort, there is an 87 - 97% probability of observing at least 1 DLT if the true DLT rate is 20-33%.

In Cohorts 3, 4, 6, [REDACTED] a subject number of 20 will provide an 88% probability of observing at least one adverse event with 10% incident rate. An exact 80% binomial confidence interval (CI) will be provided for overall response rate. With the 20 subjects and 25% overall response rate, the expected 80% CI would be 13% to 42%.

In Cohort 5, a subject number of 12 will provide a 72% probability of observing at least one adverse event with 10% incident rate. An exact 80% binomial confidence interval (CI) will be provided for overall response rate. With the 12 subjects and 25% overall response rate, the expected 80% CI would be 10% to 48%.

In Cohort 7, Cohort 8, and Cohort 9, the sample size is N~40 subjects. A subject number of N~40 subjects will provide an 87% probability of observing at least one adverse event with 5% incident rate. An exact 80% binomial confidence interval (CI) will be provided for overall response rate. With the 40 subjects and 25% overall response rate, the expected 80% CI would be 16% to 36%.

## 11.2 Analysis Sets, [REDACTED] and Covariates

[figure not shown]
### 11.2.1 Analysis Sets

The analysis of all endpoints, unless noted otherwise, will be conducted on the Safety Analysis Set defined as all subjects that are enrolled and receive at least one dose of AMG 404.

The PK Analysis Set will contain all subjects who have received at least 1 dose of AMG 404 and have at least 1 PK sample collected. These subjects **may** be evaluated for PK analysis unless the number of data points required for analysis is not enough, or significant protocol deviations have affected the data, or if key dosing or sampling information is missing.

### 11.2.2 Covariates

The relationship of covariates to efficacy endpoints **may** be explored if appropriate.

### 11.3 Adaptive Design

Dose level decisions are based on a modified toxicity probability interval design (mTPI). The mTPI was developed by Ji et al. (2010). The mTPI models the probability of toxicity for each dose level using a Bayesian model where each dose level has the same prior on the probability of toxicity, a Beta (1,1). When subjects are treated at the current dose level, the posterior probability of toxicity is updated using the observed data from this level. Dose level recommendation are made based on this posterior probability of toxicity, using three toxicity probability intervals (TPI).

- Under-dosing TPI: DLT rate from 0 to < 20%
- Target TPI: DLT rate from 20% to 33%
- Over-dosing: DLT rate > 33%

For the current dose level and after adjusting for the width of the under-dosing TPI, if the DLT rate is most likely in the under-dosing TPI then the recommendation is to dose escalate. If the DLT rate is most likely in the target TPI then the recommendation is to stay at the current level. If the DLT rate is most likely in the over-dosing TPI then the recommendation is to stop the enrollment. If DLTs are observed, the maximum tolerated dose (MTD) is the dose level with a DLT toxicity rate closest to 26.7% (Ji et al. 2010).

During enrollment and treatment at the RP2D using data from cohorts 3 and 6 and additionally using data from cohorts 7-9, objective response rate will be monitored with futility stopping rules described in Section 11.4.1.1. These futility stopping rules are selected using practical considerations.

During enrollment and treatment at the RP2D using data from cohorts 3 and 6 and cohorts 7-9, subject incidence of grade 4 treatment related adverse events will be monitored with safety stopping rules described in Section 11.4.1.1. The safety stopping rules use a Bayesian approach proposed by Thall, Simon, and Estey (1995) to terminate a cohort if the posterior probability that the subject incidence of grade 4 or higher treatment-related adverse events is greater than 20% is > 80%. The stopping boundaries assume a prior distribution of Beta (0.40, 1.60).

### 11.4 Statistical Analyses

The statistical analysis plan will be developed and finalized before database lock. Below is a summary of the timing and methods for the planned statistical analyses. To

preserve study integrity, the final analysis will be conducted and reported following the end of study, as defined in Section 6.3.1.

#### 11.4.1 Planned Analyses

##### 11.4.1.1 Interim Analysis and Early Stopping Guidelines

Safety data will be reviewed on an ongoing basis. In the dose level review meetings, Amgen, in consultation with the site investigators, will review all available cumulative data by cohort prior to making dose determination decisions. Adverse events and DLTs observed in all subjects will be evaluated continually and fully integrated into all dose level review meetings and considered in all enrollment and dosing decisions.

Additional details regarding the dose review meeting are providing in Sections 8.4.1 and 13.3.

There is a planned treatment of N~40 subjects at the RP2D with enrollment to cohorts 3 and 6. Additionally, there is a planned treatment of N~40 subjects at the RP2D with enrollment to Cohort 7, N~40 subjects enrolled to Cohort 8 and N~40 subjects enrolled to Cohort 9. For each of these cohorts (Cohort 3/6, Cohort 7, Cohort 8, Cohort 9), futility will be assessed after treating 15 and 25 subjects for at least 3 months. If the observed rate of responses is consistent with a lower than 15% response rate, enrollment and treatment at the RP2D may be terminated due to futility. For purposes of assessing futility, a response is defined as an objective response per RECIST 1.1. The guidelines for early termination due to futility are as follows:

Number of Treated Subjects	Futility Termination Guideline
15	1 or fewer responders
25	4 or fewer responders
40	Enrollment to dose expansion cohort complete

If the true response rate is 15% then these termination guidelines result in a 69.4% probability of terminating dose expansion early with an expected sample size of 26.4 subjects. If the true response rate is 30% then there is a 90% probability of continuing enrollment to N~40 total subjects.

During this enrollment and treatment at the RP2D combining data from cohorts 3, 6, 7, 8 and 9 (up to 160 total subjects enrolled) [REDACTED], Amgen will conduct evaluations of the ongoing subject incidence grade 4 or higher treatment-related adverse event rate to assess if the threshold for possible early termination of a cohort has been reached. If the threshold is met in the combined

monotherapy data of expansion cohorts 3, 6, 7, 8, and 9 enrollment to all ongoing cohorts in the study, [REDACTED], will be halted pending review of safety data by the DLRT. If the threshold is met in a specific cohort, then enrollment to the specific cohort will be halted pending review of safety data by the DLRT. After receiving the DLRT recommendation, Amgen will choose to take one of the following actions.

When overall safety threshold exceeded in combined monotherapy data of expansion cohorts 3, 6, 7, 8, and 9:

- 1) Terminate the trial
- 2) Amend the protocol to potentially improve the benefit/risk for subjects (eg, increase safety monitoring, modify dose/schedule, mandate premedication)
- 3) Continue monotherapy dose expansion cohorts and other cohorts, as appropriate, without any changes

When cohort-specific safety threshold exceeded:

- 1) Terminate enrollment to the cohort
- 2) Amend the protocol to potentially improve the benefit/risk for subjects in the cohort of concern (eg, increase safety monitoring, modify dose/schedule, mandate premedication)
- 3) Continue enrollment to the specific cohort (as appropriate) without any changes

The methods for deriving the stopping boundaries overall for the combined monotherapy data of expansion cohorts 3, 6, 7, 8 and 9, or for within a cohort are described in Section 11.3 with the stopping boundaries overall for the combined monotherapy data of expansion cohorts 3, 6, 7, 8 and 9 presented in Table 11-1 and stopping boundaries for within a cohort presented in Table 11-2. Operating characteristics with pre-specified batch size of 10 new subjects per batch are presented in Table 11-3.

(Overall the combined monotherapy data of expansion cohorts 3, 6, 7, 8 and 9) and in [Table 11-4](#) (cohort with planned sample size of 40 subjects). The operating characteristics in [Table 11-3](#) and [Table 11-4](#) provide the probability of stopping the trial early for given hypothetical true rate of grade 4 or higher treatment-related adverse events, whereas the stopping criteria in [Table 11-1](#) and [Table 11-2](#) are based on situations where the empirical evidence would result in a posterior probability of  $\geq 80\%$  that the true grade 4 or higher treatment-related adverse event rate is  $\geq 20\%$ .

**Table 11-1. Stopping Boundary Overall for Combined Monotherapy Data of Cohorts 3, 6, 7, 8, and 9 with Posterior Probability of 80% and Grade 4 or Higher Treatment-Related Adverse Event Limit of 20%**

Number of subjects	Stop study if observing this many subjects with grade 4 or higher treatment-related adverse events
10	$\geq 4$
20	$\geq 6$
30	$\geq 9$
40	$\geq 11$
50	$\geq 13$
60	$\geq 15$
70	$\geq 18$
80	$\geq 20$
90	$\geq 22$
100	$\geq 24$
110	$\geq 26$
120	$\geq 28$
130	$\geq 31$
140	$\geq 33$
150	$\geq 35$
160	Combined Monotherapy Data for Cohorts 3, 6, 7, 8 and 9 Complete

**Table 11-2. Stopping Boundary for Enrollment within Cohorts 3, 6, [REDACTED] Individually with Posterior Probability of 80% and Subject Incidence of Grade 4 or Higher Treatment-Related Adverse Event Limit of 20%**

Number of subjects treated	Stop cohort enrollment if observing this many subjects with grade 4 or higher treatment-related adverse events
5	≥ 3
10	≥ 4
20	≥ 6
30	≥ 9
40	Cohort Enrollment Complete*

\* Enrollment for cohorts 7, 8, and 9 completes after n = 40 subjects enrolled. Enrollment for cohorts 3, 6, [REDACTED] completes after n = 20 subjects enrolled. [REDACTED]. Early stopping rules (eg, at 5 or 10 treated subjects) are the same regardless of planned maximum sample size in a cohort.

**Table 11-3. Operating Characteristics with Batch Size of 10 Subjects (Combining All Monotherapy Data of Expansion Cohorts 3, 6, 7, 8 and 9)**

True grade 4 or higher treatment-related adverse event rate	Probability of early stopping of dose expansion	Average sample size of overall combined monotherapy data
0.10	2.1 %	156.9
0.15	12.7 %	143.1
0.20	46.4 %	105.8
0.25	86.4 %	58.7
0.30	98.9 %	31.5

**Table 11-4. Operating Characteristics With Batch Size of 10 Subjects (Cohort-Specific Enrollment with Maximum Cohort Sample Size of n=40 Subjects)**

True grade 4 or higher treatment-related adverse event rate	Probability of early stopping of cohort enrollment	Average cohort sample size
0.10	2.0 %	39.5
0.15	9.7 %	37.6
0.20	25.8 %	33.9
0.25	47.8 %	28.8
0.30	69.2 %	23.4

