True grade 4 or higher treatment-related adverse event rate	Probability of early stopping of dose expansion	Average sample size of overall combined monotherapy data
0.10	2.1 %	156.9
0.15	12.7 %	143.1
0.20	46.4 %	105.8
0.25	86.4 %	58.7
0.30	98.9 %	31.5

Table 7-4. Operating Characteristics with Batch Size of 10 Subjects (Cohort-Specific Enrollment With Maximum Sample Cohort Size of n=40 Subjects)

True grade 4 or higher treatment-related adverse event rate	Probability of early stopping of cohort enrollment	Average cohort sample size
0.10	2.0%	39.5
0.15	9.7%	37.6
0.20	25.8%	33.9
0.25	47.8%	28.8
0.30	69.2%	23.4

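### Table 11-4 (SAP Table 7-4) omits the look at 5 subjects that Table 11-2 (SAP Table 7-2) prescribes, so it slightly understates the chance of a cohort halt and slightly overstates average cohort size

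*Protocol*

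**What the plan says.** Protocol section 11.4.1.1 gives the cohort-level safety boundary in Table 11-2. The column headed "Stop cohort enrollment if observing this many subjects with grade 4 or higher treatment-related adverse events" lists at least 3 at 5 treated subjects, 4 at 10, 6 at 20 and 9 at 30, with enrollment complete at 40. The footnote adds: "Early stopping rules (eg, at 5 or 10 treated subjects) are the same regardless of planned maximum sample size in a cohort". It also says: "Enrollment for cohorts 7, 8, and 9 completes after n = 40 subjects enrolled". Cohorts 3 and 6 complete at 20.

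The text before the tables says: "Operating characteristics with pre-specified batch size of 10 new subjects per batch are presented in" Tables 11-3 and 11-4, the second of these being for a cohort planned at 40. Table 11-4 is titled "Operating Characteristics With Batch Size of 10 Subjects (Cohort-Specific Enrollment with Maximum Cohort Sample Size of n=40 Subjects". SAP section 7.1 repeats the boundary as Table 7-2 and the operating characteristics as Table 7-4, titled "Operating Characteristics with Batch Size of 10 Subjects (Cohort-Specific Enrollment With Maximum Sample Cohort Size of n=40 Subjects", with the same figures.

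**The concern.** Table 11-4 is offered as the behavior of the rule in Table 11-2, but the two tables have different first looks. The rule can halt a cohort after 5 subjects; the calculation cannot halt one before 10. A reader would expect the printed halting probabilities and average sizes to belong to the prescribed rule, and nothing in either document warns otherwise. These are the only stated properties of the cohort-level safety rule in a first-in-human study, so the record should describe the rule as written, even if the difference is small.

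**Working it through.** **Inputs.** Boundaries from Table 11-2: 3/5, 4/10, 6/20, 9/30, maximum 40. Prior Beta(0.40, 1.60) and posterior threshold of 80% for a rate above 20%, from protocol section 11.3. True rates and printed figures from Table 11-4.

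**Is the look at 5 part of the same rule?** With r events in n subjects the posterior is Beta(0.40 + r, 1.60 + n − r). The posterior probability that the rate exceeds 20% is 0.948 at 3 of 5 and 0.778 at 2 of 5. Three is therefore the first count above 0.80, and the n = 5 boundary follows from the stated prior just as the later ones do.

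**Method.** Exact binomial recursion. At each look, convolve the distribution of events so far with the binomial distribution for the new subjects. Record the probability at or above the boundary as a halt at that look, then remove those paths. The halting probability is the sum of the halts over looks. Average size = Σ n × P(halt at n) + 40 × P(no halt).

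**Worked example, true rate 0.20.**

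- Looks at 10, 20, 30: halts 0.1209 + 0.1109 + 0.0262 = 0.258 after rounding. Average size = 10 × 0.1209 + 20 × 0.1109 + 30 × 0.0262 + 40 × 0.7421 = 33.9. Table 11-4 prints 25.8% and 33.9.
- Looks at 5, 10, 20, 30: halts 0.0579 + 0.0797 + 0.1055 + 0.0254 = 0.2685. Average size = 5 × 0.0579 + 10 × 0.0797 + 20 × 0.1055 + 30 × 0.0254 + 40 × 0.7315 = 33.2.

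**All rates** (halting probability / average size):

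| True rate | Printed | Looks 10, 20, 30 | Looks 5, 10, 20, 30 | Change from adding n = 5 |
|---|---|---|---|---|
| 0.10 | 2.0% / 39.5 | 2.05% / 39.47 | 2.49% / 39.29 | +0.44 points / −0.18 |
| 0.15 | 9.7% / 37.6 | 9.73% / 37.62 | 10.59% / 37.20 | +0.86 / −0.42 |
| 0.20 | 25.8% / 33.9 | 25.79% / 33.89 | 26.85% / 33.22 | +1.06 / −0.67 |
| 0.25 | 47.8% / 28.8 | 47.73% / 28.77 | 48.66% / 27.84 | +0.93 / −0.93 |
| 0.30 | 69.2% / 23.4 | 69.20% / 23.41 | 69.83% / 22.23 | +0.63 / −1.18 |

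The looks at 10, 20 and 30 reproduce all ten printed figures to within 0.1. An extra look at 40 (11 or more events) does not explain them: at a true rate of 0.20 it gives 29.5% without the look at 5 and 30.5% with it.

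**Why the change is small.** At a true rate of 0.30, 16.3% of cohorts reach 3 of 5, yet the look adds only 0.63 points. About (16.3 − 0.63)/16.3 = 96% of those cohorts would have halted at 10, 20 or 30 anyway. The look mainly brings halts forward, so average size moves more than halting probability there.

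**Table 11-3 is unaffected.** Table 11-1 has no look at 5, and the combined-data figures reproduce (46.39% and 105.79 at 0.20, against the printed 46.4% and 105.8).

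**The case against.** The strongest reply is that Table 11-4 contains no arithmetic error. Its title and the text both state a batch of 10, and its figures are right under that assumption. It covers three of the four looks with their exact boundaries. The effect is small and in the conservative direction: the actual rule halts slightly sooner than stated. Crossing a boundary only pauses enrollment until the dose level review team has looked at the data, after which the sponsor may continue unchanged. Amendment 6 also discontinues trial activities, so the table has little prospective use.

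All of that stands, and it sets the severity. It does not remove the mismatch: stating a batch of 10 does not tell the reader that a prescribed look was left out.

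Three stronger readings might be inferred, and the documents do not support them.

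- *The printed figures also misstate the 20-subject cohorts.* Both the text and the title limit Table 11-4 to cohorts of 40, so it makes no claim about Cohorts 3 and 6. A panel for them would be an addition.
- *Halting is about half as likely in those cohorts.* With looks at 5 and 10 only, the ratio to the 40-subject rule is near half from a true rate of 0.20 upward (13.77/26.85 = 51%). At 0.10 it is 1.76/2.49, about 70%, and at 0.15 it is 6.08/10.59 = 57%.
- *The table overstates how many subjects are exposed before a halt.* The average-size column includes cohorts that never halt and run to 40, so it does not measure that.

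**Conclusion.** The point holds as a minor inconsistency. Table 11-4 and SAP Table 7-4 describe looks at 10, 20 and 30, while the prescribed rule also looks at 5. The omission understates the halting probability by 0.4 to 1.1 percentage points and overstates average cohort size by 0.2 to 1.2 subjects over true rates of 0.10 to 0.30. Nothing in this changes a boundary, a sample size or a judgment on whether the rule is acceptable.

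The figures assume independent subjects with a common event rate, data complete at each look, and a halt counted as a stop. The last assumption reproduces the printed table, although in practice a halt is a pause for review.

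**What to change.** Restate protocol Table 11-4 and SAP Table 7-4 for looks at 5, 10, 20 and 30 with a maximum of 40:

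| True rate | Probability of early stopping | Average cohort size |
|---|---|---|
| 0.10 | 2.5% | 39.3 |
| 0.15 | 10.6% | 37.2 |
| 0.20 | 26.9% | 33.2 |
| 0.25 | 48.7% | 27.8 |
| 0.30 | 69.8% | 22.2 |

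In both titles, replace the batch size with looks at 5, 10, 20 and 30 subjects, and adjust the batch-size sentence in the text for this table. Leave Tables 11-1, 11-2 and 11-3 and their SAP copies as they are.

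Optionally, and for information only, add the values for cohorts with a maximum of 20 (looks at 5 and 10): 1.8/6.1/13.8/24.5/37.3% at the same true rates.

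The cost is two restated tables and one sentence in each document. Conduct does not change, and the stated chance of a halt at a true rate of 0.10 rises from 2.0% to 2.5%.
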